1.5.1. ClinicalTrials.gov. The University of Pittsburgh is strongly committed to supporting compliance with the NIH Policy on the Dissemination of NIH-Funded Clinical Trial information. As such, the University of Pittsburgh Office for ClinicalTrials.gov (<http://rcco.pitt.edu/clinicaltrialsgov>) provides resources and procedures to assist Responsible Parties with fulfilling the requirements for submission of clinical trial information to ClinicalTrials.gov. Monitoring by the University of Pittsburgh Institutional Review Board (IRB) and Research Conduct and Compliance Office (RRCO) ensures that all clinical trial registrations and results information are obtained in compliance with NIH policy requirements and reported on ClinicalTrials.gov. Per NIH's requirements, the PI will register the proposed clinical trial on ClinicalTrials.gov no later than 21 days after the first participant is enrolled. The PI will also ensure that summary results from the proposed clinical trial are submitted to ClinicalTrials.gov for public posting no later than one year after the trial's primary completion date. Per NIH's policy, this summary information will include participant flow, demographic and baseline characteristics, outcomes and statistical analyses, adverse events, the protocol, statistical analysis plan, and administrative information. Clinical trial information submitted to ClinicalTrials.gov will be verified, updated, and corrected in accordance with all applicable deadlines established in the Final Rule for Clinical Trials Registration and Results Information Submission (42 CFR 11.64). Informed consent documents will also include a specific statement relating to posting of clinical trial information at ClinicalTrials.gov.

1.5.2. Publications. Findings from the proposed study, including baseline observations and intervention outcomes, will be published to scientific journals with broad audiences. I will specifically target journals specializing in health psychology, sports medicine, behavioral medicine, and clinical science. Examples include Psychosomatic Medicine, Health Psychology, Translational Behavioral Medicine, and Clinical Journal of Sports Medicine.

1.5.3. Presentations at meetings. Results from the proposed study will be presented at annual scientific meetings of the Society for Behavioral Medicine, American Psychosomatic Society, and American Psychological Association. I will also present findings at local conferences and symposia, such as the Health Psychology brown bag series at the University of Pittsburgh. As appropriate, findings may also be shared at public community events in an effort to engage the public in scientific discussions and provide information about research activities occurring at the University.

1.5.4. Websites. The Department of Psychology maintains an active website where faculty research findings and accomplishments are highlighted, and announcements for scientific presentations are posted. As findings emerge from the proposed study, they may be featured on the departmental website. In addition, in collaboration with staff members in [name] lab with web programming experience, I will create a website dedicated to the proposed study. This website will serve as a public access point for information about the study, including details about the study protocol, any publications or presentations based on findings obtained from the study, and information about how to participate.

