programmed to connect users with a trainer via an app. We will recruit individuals between the ages of 30-55 years ($N = 20$) from a well-characterized cohort of adults in Jamaica with early-childhood exposure to malnutrition and other forms of ELA (e.g., poverty) confirmed by contemporaneous medical records who continue to participate in research led by Co-Investigators and Reversibility Network members [name] and [name]. A comparison sample ($N = 20$) of age, sex, and race matched adults with an ELA history will be recruited in Pittsburgh, and a harmonized battery of cognitive, fitness, and psychosocial measures will be collected in both samples at baseline and following the 12-week intervention.

We have assembled a highly creative, productive, and interdisciplinary team with extensive experience conducting exercise interventions and evaluating indicators of brain health in multiple vulnerable populations (e.g., older adults with cognitive impairment, adults with a history of malnutrition). We will test the following aims:

Aim 1: Determine the feasibility and acceptability of a remote PA intervention among adults exposed to threat-related ELA living in Pittsburgh and Jamaica. It is hypothesized that the remote format of the intervention will enhance the feasibility of conducting a PA trial among individuals with a history of threat-related ELA.

Aim 2: Determine whether the remote PA intervention promotes improvements in cognitive and psychological functioning. It is hypothesized that cognitive and psychological functioning will improve over the course of the intervention and improvements will be greatest among those with the highest adherence rates.

The proposed research addresses the central goal of the NIA Reversibility Network to develop and test feasible interventions that may mitigate ELA-related risk for adverse health outcomes in adulthood. This pilot feasibility trial will set the groundwork for a larger-scale future R01 application that will test the efficacy of a remote PA intervention for improving brain health among adults who have been exposed to ELA. Further, the proposed research will provide an initial test of the impact of country-level factors (e.g., poverty rates, prevalence of more severe ELA such as malnutrition) on ELA-related disease burden in adulthood, information which may be leveraged to tailor interventions to meet the specific needs of the target population.

1.1 Overview of Methods:

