1.1.1. Subject recruitment, Pittsburgh: We expect to advertise through numerous outlets in order to enhance our ability to successfully recruit for the study. Participants ($N=20$) will be recruited via methods found to be effective in other studies, including the University of Pittsburgh online research registry (Pitt+Me) and community presentations at local community centers. We will also advertise on the Brain Aging and Cognitive Health (BACH) lab website (<http://bachlab.pitt.edu/>), lab social media accounts (Facebook & Instagram), and will post flyers and other ads around the Pittsburgh community.

1.1.2. Subject recruitment, Jamaica: Participants ($N=20$) will be recruited from across Jamaica, particularly from the areas within and surrounding Kingston, Jamaica where the University of the West Indies is located. Participants will be age, sex, and race matched across sites.

1.1.3. Eligibility criteria: Inclusion criteria will be as follows: 1) adults aged 30-55 years, 2) exposure to at least one form of threat-related ELA (e.g., exposure to violence; physical abuse) prior to the age of 10 as documented by retrospective self-report (described in detail below), 3) self-identified Black or African American race, 4) access to high-speed internet, and 5) sedentary lifestyle (<60 minutes of PA/week). Exclusion criteria will include: 1) psychosis, 2) significant suicide risk (i.e., current, active suicidal ideation with a plan), 3) engaging in moderate-intensity exercise >=20 min per day, >=3 times per week, 4) current treatment for cancer, 5) neurological condition (e.g., MS, Parkinson's, Dementia, MCI) or brain injury (e.g., stroke), 6) substance use disorder in the past 3-months, 7) current treatment for congestive heart failure, angina, uncontrolled arrhythmia, DVT or other cardiovascular event, 8) myocardial infarction, coronary artery bypass grafting, angioplasty or other cardiac condition in the past year, 9) sensory impairment that would preclude neuropsychological testing, 10) not fluent in English, 11) travelling consecutively for 2+ weeks during the study, 12) uncontrolled hypertension, 13) insulin-dependent Diabetes Mellitus, and 14) self-identified as any race other than Black or African American.

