A study team member will check-in with participants via weekly emails or calls with participants via phone or HIPAA-compliant videoconferencing software to troubleshoot issues that arise during exercise, discuss participants' subjective exercise experience, and problem-solve barriers to adherence. The format of these check-ins will be determined by the participant's preference, progress, and needs, and may change over the course of the intervention as warranted. Exercise safety will also be reviewed during these weekly check-ins and participants will be encouraged to reach out to the study staff if any safety-related concerns arise. Participants will also be asked about whether there have been any issues with their bike or other equipment. Should damage occur, two staff people will schedule a time to visit the participants home to fix the issue(s) noted or to collect the bike to be returned to the manufacturer for repair. In the event that the bike must be returned to the manufacturer for repair, participants will be furnished with a replacement bike within 5 days of the removal of the original bike, and any exercise sessions missed as a result will either be made up within the following week or marked as absences that will not be counted toward the participant's attendance/adherence bonus numbers.

1.1.13. Follow up assessment: All of the baseline assessments will be repeated at follow-up after completing the 12-week intervention, including cognitive and psychological functioning, and physical activity monitoring (see descriptions above). We will not administer CTQ or MACE questionnaires at follow-up given that scores on these questionnaires should not change.

1.1.14. Bike return: Following the completion of the 12-week intervention, the study PI and a staff member will return to participants' homes to collect the study-issued

stationary bike, tablet, and heart rate monitor. Any needed repairs will be made and equipment will be cleaned for use by another participant.

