1.2. Statistical Analysis Plan: This intervention is a pilot feasibility investigation. Therefore, the primary focus is on evaluating how successful we are at recruitment and retention, and whether we are able to keep participants engaged in the intervention. Although we will evaluate the effect of the intervention on cognitive and psychological functioning, is not intended to be statistically powered to address questions regarding the effectiveness of the intervention for improving the outcomes among adults exposed to early life adversity.

Aim 1a. The feasibility of this intervention will be assessed by examining average adherence rate over the course of the intervention, operationalized as a combination of number of sessions attended and average duration of each session. Average number of minutes spent in the 'moderate-intensity' heart-rate zone per session will also be examined. Threshold analysis will be conducted to understand whether exercise adherence declines after a certain time point in the intervention (e.g., 6-weeks). In an exploratory analysis, ActiGraph data will be used to assess whether engagement in the intervention results in an increase in physical activity from pre- to post-intervention.

Aim 1b. Intervention acceptability will be assessed through a self-report questionnaire completed post-intervention, including questions about satisfaction with various aspects of the intervention (i.e., intervention duration, interaction with study staff, use of technology to remotely guide intervention, overarching feedback about intervention, willingness to continue engaging in exercise).

Data related to 1) study enrollment and 2) summaries of weekly video/phone calls to monitor exercise adherence and engagement will be documented. The recruitment process (e.g., proportion of participants screened who enrolled in the study) and participants' experience in the intervention based on weekly phone sessions and the satisfaction questionnaire at the completion of the study will be qualitatively examined.

Aim 2. Paired sample T-tests will be used to assess change in cognitive and psychological functioning over the course of the 12-week intervention.

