Aim 3: Attendance and adherence rates, as well as participant satisfaction ratings, will be compared using Paired sample T-tests to determine whether there are differences in these metrics across sites. Statistical tests performed to assess Aim 2 will be repeated separately for each site to evaluate whether effect sizes differ by site.

1.3. Minimization of Risks:

1.3.1. To reduce the risk for breach of confidentiality we will separate all information obtained during the screening period from identifying documents. All research data will be de-identified. These documents will be stored in a separate location from the data and the screening information in locked filing cabinets in a locked and secure room that only lab personnel have access to. Data that is saved electronically (computer system) is protected by the University of Pittsburgh firewalls. Regarding heart rate data collected via the Polar app, these data will only

be stored on the app temporarily (i.e., during the exercise session) in order to continuously monitor safety. This information will be transferred to our secure server as soon as possible after each session to minimize risk of breached confidentiality.

- 1.3.2. Subject privacy will be maintained in this research study by having all participants answer questions and perform cognitive tasks in an isolated and private room. All of the information that we will collect in this protocol is essential for the research questions we are posing. In this way, there will be no unnecessary personal information collected from these participants.

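### Aim 2 asks whether the intervention improves cognition and mood, but a before-after test with every participant exercising cannot separate exercise from practice, time, expectancy or staff contact

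*Combined protocol and SAP*

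**What the plan says.** Section 1.0 words the aim causally: "Aim 2: Determine whether the remote PA intervention promotes improvements in cognitive and psychological functioning". Its hypothesis adds that "improvements will be greatest among those with the highest adherence rates".

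Section 1.2 (Statistical Analysis Plan) opens a sentence with "Although we will evaluate the effect of the intervention on cognitive and psychological functioning" and ends it by saying that the study is not meant to be powered for questions of effectiveness. The analysis it gives for Aim 2 is: "Paired sample T-tests will be used to assess change in cognitive and psychological functioning over the course of the 12-week intervention". Under Aim 3 the same tests are repeated within each site, to see whether what the plan calls *effect sizes* differ.

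On who is treated, section 1.0 says "A comparison sample ($N = 20$) of age, sex, and race matched adults with an ELA history will be recruited in Pittsburgh" and section 1.1.2 says "Participants ($N=20$) will be recruited from across Jamaica". Aim 1 covers the remote intervention in both places, and Aim 3 says "Attendance and adherence rates, as well as participant satisfaction ratings, will be compared using Paired sample T-tests to determine whether there are differences" across sites.

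On measurement, section 1.1.13 says "All of the baseline assessments will be repeated at follow-up after completing the 12-week intervention, including cognitive and psychological functioning, and physical activity monitoring"; only the two childhood-adversity questionnaires (CTQ and MACE) are left out at follow-up.

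**The concern.** The aim asks a causal question, and section 1.2 refers to an effect of the intervention. The test behind both measures only how far scores moved between two visits. That movement includes anything else that happened over the same 12 weeks.

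The rival explanations differ by outcome. The NIH Toolbox measures in section 1.1.8.1 are mostly performance tasks (card sorting, list sorting, picture sequence, flanker, pattern comparison), for which a second exposure may itself raise the score. The stress, anxiety, depression and affect scales in section 1.1.7.1 are open to time trends, to expectancy in people who know they are being treated, and to the weekly staff contact in section 1.1.12.

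If the plan is followed as worded, an intervention with no effect on these outcomes could be reported as improving them.

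**Working it through.** **Step 1. Is there an untreated comparison?** The plan describes no randomisation and no wait-list, attention or untreated group. The Pittsburgh group is called a comparison sample, but attendance, adherence and satisfaction are compared between sites, which requires both to receive the intervention. There are 20 + 20 = 40 participants, all exercising. The site contrast cannot act as a control.

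**Step 2. Is non-exercise change handled in another way?** The plan mentions no alternate forms, practice run-in, second baseline or practice adjustment. The adherence hypothesis could give weak internal evidence, but section 1.2 specifies no analysis for it, and adherence is self-selected.

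**Step 3. What does the paired test estimate?** For any one outcome,

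expected mean change = exercise effect + practice + time trend + expectancy and contact.

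With one group and two visits, only the sum is estimable. Sample size does not appear in the expression, so more participants narrow the interval around the same sum.

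**Step 4. How often could practice alone reach significance?** The plan gives no alpha, SD, correlation or practice gain, so there is no figure to reproduce. All inputs below except n are assumptions:

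- exercise effect zero; practice gain g = 0.1 to 0.4 baseline SD; equal SDs at both visits
- pre-post correlation r = 0.7 (0.6 and 0.8 as a check)
- two-sided alpha 0.05
- n = 40 pooled or n = 20 for one site, with everyone completing both visits

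SD of change = √(2(1 − r)) = √0.6 = 0.775 baseline SD at r = 0.7. Standardised change dz = g / 0.775. The test statistic is noncentral t with n − 1 degrees of freedom and noncentrality dz × √n. The chance of a significant improvement is the probability that it exceeds the upper 2.5% point of central t (2.023 for n = 40, 2.093 for n = 20).

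| Practice gain g (SD) | dz | n = 40 | n = 20 |
|---|---|---|---|
| 0 | 0 | 2.5% | 2.5% |
| 0.1 | 0.129 | 12% | 8% |
| 0.2 | 0.258 | 36% | 19% |
| 0.3 | 0.387 | 67% | 38% |
| 0.4 | 0.516 | 89% | 59% |

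Example: g = 0.3 and n = 40 gives noncentrality 0.387 × √40 = 2.45, and a probability of 0.666.

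Sensitivity to r: at g = 0.3 and n = 40, r = 0.6 gives 54% and r = 0.8 gives 83%.

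**Step 5. Bias or low power?** Keep g = 0.3 and r = 0.7 and change only n: 38% at 20, 67% at 40, 93% at 80. The false-positive rate rises with sample size, which is how bias behaves.

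The table covers the performance-based cognitive tasks only. For the self-report scales the argument is Step 3, and no size is offered.

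**The case against.** The strongest defence is that this is an open feasibility pilot. Section 1.2 makes recruitment, retention and engagement the primary focus, disclaims power for effectiveness, and section 1.0 leaves efficacy to a later trial. The sentence specifying the Aim 2 test speaks only of change over the 12 weeks, and the hypothesis speaks of improvement over the course of the intervention. On this view the causal language is confined to the aim itself and one clause of the SAP.

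Much of that stands. It limits the point to wording and interpretation, and it means that a single-arm pilot is not in itself a fault. It does not answer the point, because the disclaimer concerns precision, and a reader could take it to mean that the same design with more people would settle the question.

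The percentages are also fairly challenged. They depend on assumed inputs and full retention, and they are clearly lower for the site-level tests. The argument in Step 3 does not depend on them.

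Two stronger readings are tempting. A reader might infer that the Aim 2 change is meant to be the effect size for the future R01. The protocol says only that the trial will lay the groundwork for that application, which may as well mean recruitment and adherence. A reader might also look to Picture Vocabulary as a built-in negative control. Practice differs by task, so subtracting its change could leave most of the practice gain elsewhere while appearing to adjust for it. Section 1.1.8.1.1 also lists it only among tasks that may be given, and it says nothing about the psychological scales.

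**Conclusion.** The point holds as one of attribution. As worded, Aim 2 cannot be met by the planned design and test, and the power caveat in section 1.2 does not cover this. The conclusion follows from three features of the plan: all participants treated, one assessment before and one after, and a paired test alone.

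The size is illustrative. With no exercise effect, the chance of a significant improvement per task could run from about 12% to 89% pooled and 8% to 59% at one site, against 2.5% nominal. This rests on assumed practice gains of 0.1 to 0.4 SD, r = 0.7, alpha 0.05 and complete follow-up.

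It should be corrected, because it changes what the trial may conclude. It does not touch the primary feasibility aim, and the documents do not show that the Aim 2 estimate is planned as the effect size of a later trial.

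**What to change.** 1. In section 1.0, reword Aim 2 to: *estimate the change in cognitive and psychological functioning over the 12-week intervention period*.
2. In section 1.2, replace *effect of the intervention*, and *effect sizes* in the site comparison under Aim 3, with *pre-post change*.
3. Report each change with a 95% confidence interval, pooled and by site.
4. State in the SAP that change is not attributed to exercise because there is no concurrent control, naming practice for the cognitive tasks and time trends, expectancy and staff contact for the self-report scales.
5. Add that, if the change is used in planning the later efficacy trial, it must not be taken as an exercise effect.

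The cost is a few sentences and a more modest Aim 2 claim, with no new data or participants. A control arm is not requested. A 20 v 20 comparison of change scores would cancel any shared change, but at 80% power it would detect only about 0.91 SD of change, and its power at 0.5 SD would be about 34%.

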1.1.9. Activity monitoring: At the end of the baseline assessment visit, eligible participants will be fitted with a commercially available physical activity monitoring device (ActiGraph Link), worn on the wrist. ActiGraph Link provides information about movement, rotation, and body position, that is used to determine intensity and amount of physical activity. Activity monitoring will be completed one-week prior to and one-week after completion of the intervention.

1.1.10. Exercise training session: After completion of the initial assessment visit and the activity monitoring period, two study team members will schedule a time to transport a study stationary bike to the participant's home via a university-owned vehicle, set-up the bike in the participant's home, and monitor the participant's first home-based exercise session in-person. Participants will also be provided with a study-owned tablet loaded with the application (described below) that will be used to administer and monitor their exercise regimen throughout the intervention.

1.1.11. Participants will complete one onsite exercise session, during which they will work with the exercise physiologist to determine the appropriate peddling speed corresponding to a moderate-intensity exercise zone based on the American College of Sports Medicine Guidelines. Heart rate and blood pressure will be monitored during this session to ensure that the participant does not exceed ACSM guidelines for safe activity.

1.1.12. Exercise intervention: The intervention will use personalized physical activity regimens that are remotely administered by exercise staff using an application called Neotiv. Neotiv has been programmed by a research group in Germany who have agreed to make it freely available for this pilot study. Neotiv is integrated with the stationary bike, allowing for the collection of data about speed, resistance, and duration of cycling. We will use Neotiv to monitor adherence to the intervention protocol and to adjust the protocol as needed. The participant will complete three exercise sessions per week on the bike at home for 12-weeks, which will gradually increase in duration from 15- to 50-minutes over the first month of the intervention. The final weekly exercise goal will be set to 150 minutes.

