Prior to initiating each exercise session, the participant will wear a Polar heart rate monitoring band around their chest, open the Neotiv application on the study tablet, at which time they will be prompted to rate their current mood using the Exercise

Induced Feeling Inventory (EFI)³⁰, which prompts respondents to rate the extent to which 12 different emotion words describe how they feel in the moment on a scale from 0 (“Do not feel”) to 4 (“Feel very strongly”). Example words include “Calm”, “Tired”, “Revived”, “Happy”, and “Fatigued”. The participant will then press the start button on the tablet application and begin exercise, at which time data from the exercise bike and the heart rate monitor will begin continuous transfer to the tablet in one-second intervals, via Bluetooth and ANT+ technology. Pleasant and relaxing images will be presented via the tablet during the exercise sessions to maintain interest and adherence. At the end of each exercise session, participants will be prompted to again rate their mood on the EFI and to rate their perceived exertion using the Borg scale from 6 to 20. After completion of the session the participant will press the end button on the tablet application and put the tablet in standby mode, unplug the stationary bike, and engage in 10-minutes of a stretching regimen taught by the exercise physiologist during the training session.

After completion of each exercise session, the following data will be sent to a subject-folder (named by study id) on a secure cloud-based platform (google firebase database set up for the study), which will be accessible to study staff: 1) heart rate per second 2) bike resistance per second, 3) peddling speed (rotations per minute), and 4) duration of exercise session. Study exercise staff will review these exercise data on a daily basis to monitor intervention adherence and will modify the exercise regimen (i.e., bike resistance) as required to ensure the participant is engaging in moderate-intensity exercise for the majority of each exercise session.

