However, to reduce the risk of heart troubles during exercise, participants with a history of heart disease will be ineligible to participate in this study. The study will follow ACSM guidelines in regards to contraindications to perform exercise, including systolic blood pressure > 190 mm Hg, diastolic blood pressure > 100 mm Hg, or heart rate > 100 beats per minute. These parameters will be evaluated during the exercise training session prior to the start of the intervention and participants will be disqualified if they exceed these recommendations. Once the intervention has begun, heart rate will be routinely monitored by exercise staff. If heart rate is observed to be abnormally high during home-based exercise sessions, exercise staff will contact the participants to discuss concerns and modify the exercise protocol as appropriate. If excess heart rate continues after modifications, exercise may be discontinued until the participant has been evaluated by a physician and has provided documentation of medical clearance to continue.

- 1.3.7. Exercise staff have completed a degree in Exercise Science or related field (e.g., kinesiology) and / or have a fitness certification from a reputable organization. All staff will have a minimum of 2 years of experience in exercise supervision and prescription. The exercise prescription level is moderate in intensity and the risk of a cardiac event occurring during exercise is 1 in 400,000 – 800,000 hours of exercise. Given this low level risk, it is not feasible to have a physician on site at each exercise session. All staff involved in the exercise intervention will review the emergency protocol of the hosting community centers. In addition, each session is staffed by individuals who are trained and certified in First-Aid, CPR, and AED use and oxygen administration. Both centers have first-aid kits, AED's and oxygen available at all times. Subjects will start with 10 - 15 minutes of moderate exercise and gradually increase as they can tolerate more. Level of increase will be individually based. This gradual increase is done to prevent injury. If subject becomes injured, they will need clearance from their physician in order to return to the intervention.

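### Aim 2 predicts the largest gains in the most adherent participants, but no analysis in the SAP relates adherence to change in cognitive or psychological scores

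*Combined protocol and SAP*

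**What the plan says.** Section 1.0, Aim 2, hypothesises that cognitive and psychological functioning will improve over the intervention and that "improvements will be greatest among those with the highest adherence rates".

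Section 1.2 gives Aim 2 a single sentence: "Paired sample T-tests will be used to assess change in cognitive and psychological functioning over the course of the 12-week intervention". Aim 3 repeats those tests separately for each site.

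Adherence appears in the SAP in other roles. Under Aim 1a it is a feasibility outcome, "operationalized as a combination of number of sessions attended and average duration of each session", with a further analysis of whether it falls off after some time point. Under Aim 3 it is an outcome compared between sites: "Attendance and adherence rates, as well as participant satisfaction ratings, will be compared using Paired sample T-tests".

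The raw data for an adherence score are collected. Section 1.1.12 has session data sent to a study database after each session, and "Study exercise staff will review these exercise data on a daily basis to monitor intervention adherence".

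The SAP preamble calls the study a pilot feasibility investigation that is not powered for effectiveness, but still says the intervention's effect on cognitive and psychological functioning will be evaluated.

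**The concern.** Half of a stated hypothesis has no analysis. If the plan is followed exactly, the trial ends without an estimate of how change varies with adherence, although the data to make one will exist.

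The likelier outcome is that someone runs the analysis after the data are in, because the pilot is meant to prepare a larger application. At that point nothing fixes the adherence score: the SAP calls it a combination of two quantities and gives no rule for combining them. With several candidate scores and about 13 outcomes, there is room to report the pairing that looks best.

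A smaller matter of wording belongs with this. The SAP's Aim 2 sentence correctly speaks of assessing change. The Aim 2 statement in section 1.0 and the preamble of section 1.2 go further and speak of the intervention promoting improvement or having an effect. Everyone receives the exercise programme and takes the same battery twice, so the paired test estimates change over 12 weeks and cannot separate exercise from practice on the tests or from anything else that changed in that time.

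**Working it through.** The plan states no figure for this analysis, so there is none to reproduce. The main check is textual, followed by two calculations for context.

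**1. Does any planned analysis link adherence to change in scores?**

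| Analysis | Role of adherence | Outcome |
|---|---|---|
| Aim 1a, average adherence and heart-rate-zone minutes (1.2) | outcome | adherence |
| Aim 1a, threshold analysis (1.2) | outcome, over time | adherence |
| Aim 1a, exploratory ActiGraph (1.2) | none specified | physical activity |
| Aim 2, paired t-tests (1.2) | none | cognitive and psychological change |
| Aim 3, site comparison (1.2) | outcome, by site | attendance, adherence, satisfaction |
| Aim 3, Aim 2 tests repeated (1.2) | none; split by site | cognitive and psychological change |
| Exploratory adversity analysis (1.1.6.1) | none; split by type of adversity | not specified |

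No row has adherence as predictor, covariate, moderator or stratifier of cognitive or psychological change. A paired t-test uses only the two scores per person, so it cannot address the adherence clause.

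**2. How precise would the missing analysis be?**

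Inputs: 20 participants per site, 40 in total (section 1.1). Assumptions: an observed partial correlation of 0.30 between adherence and follow-up score, two covariates (baseline score and site), and losses of 0%, 10% and 20%. The documents state no dropout rate.

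Formula: 95% CI = tanh(atanh(0.30) ± 1.96/√(n − 5)), with atanh(0.30) = 0.3095.

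- n = 40: 0.3095 ± 0.3313, giving -0.02 to 0.57
- n = 36: 0.3095 ± 0.3520, giving -0.04 to 0.58
- n = 32: 0.3095 ± 0.3772, giving -0.07 to 0.60

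Even with no losses the interval runs from no association to a strong one. This supports estimation, not testing.

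Number of slopes: six NIH Toolbox tasks are listed (1.1.8.1.1). Section 1.1.7.1 gives about seven psychological scores (PSS 1, STAI 2, CES-D 1, PANAS 2, race-related stress 1), so about 13 in all. With no true association, 13 × 0.05 = 0.65 intervals would be expected to exclude zero by chance.

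**3. Does the choice of adherence score matter?**

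Section 1.1.12 sets three sessions a week for 12 weeks (36 sessions), "which will gradually increase in duration from 15- to 50-minutes over the first month of the intervention". Assume weekly steps of 15, 26.67, 38.33 and 50 minutes, then 50 throughout.

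- Person A completes every session in weeks 1 to 4, then stops: 12 sessions, 3 × (15 + 26.67 + 38.33 + 50) = 390 minutes.
- Person B completes one full session a week for 12 weeks: 12 sessions, 130 + 8 × 50 = 530 minutes.

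Scored as the mean of actual over planned duration with missed sessions as zero, both get 12/36 = 0.33. Scored as total minutes, B has 530/390 = 1.36 times A's exposure. Both are reasonable scores and they order these two people differently. The SAP's wording does not choose between them.

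**The case against.** The strongest reply is that this is a feasibility pilot. Section 1.2 puts recruitment, retention and engagement first and disclaims power for effectiveness, and section 1.0 leaves efficacy to a later trial. The Aim 2 statement and the first half of its hypothesis do have an analysis; only one clause lacks one. The added slope would be imprecise and confounded by self-selection. All of this stands and limits the severity. It does not remove the point: a disclaimer about power excuses wide intervals, not the absence of any analysis for a stated hypothesis. Nor does it deal with attribution, which a larger sample without a control group would not cure.

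Three stronger readings are tempting, and the documents do not support them.

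- A reader might infer that average session duration is an unsuitable ingredient because, with a rising schedule, early stopping lowers both the session count and the average. That depends on who stops and when, which the documents do not say. Simulating 40 people on the ramp assumed above, with attendance probability uniform between 0.4 and 1, the mean correlation between sessions attended and average duration is about 0 with no early stoppers, 0.57 if 20% draw a random stopping week, and 0.77 if everyone does. Section 1.1.13 places follow-up after the 12 weeks and does not say that early stoppers return, so they may not enter the regression at all.
- A reader might infer that scoring against planned length is the correct choice. If the clause is read as a dose hypothesis, actual minutes are equally legitimate.
- A reader might infer that bike-repair absences distort adherence. Section 1.1.12 first allows missed sessions to be made up within the following week. Only otherwise are they "marked as absences that will not be counted toward" the bonus numbers. The documents give no repair frequency, so no size can be put on this.

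**Conclusion.** The point holds as a mismatch between hypothesis and SAP: Aim 2 makes a prediction about adherence that no planned analysis can address. It rests on the text alone and needs no assumption. Severity is minor to moderate, because Aim 2 is secondary to feasibility and Aim 1 is untouched.

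What the missing analysis could deliver is modest. At an assumed observed partial correlation of 0.30, the 95% CI with all 40 pairs just includes zero, and it widens with loss. The slope would be observational and limited to people with follow-up data. The undefined adherence score matters here only because it leaves a choice open until after the data are seen; the documents do not show that any particular score is wrong.

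The attribution wording is a genuine but smaller correction. The planned test is a valid estimate of pre-post change, but describing that change as an effect of the intervention goes beyond a single-arm design with a repeated battery.

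**What to change.** Choose one of two routes.

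**Route A: add the analysis.** Add a paragraph to Aim 2 in section 1.2, labelled exploratory and observational:

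1. Regress each follow-up score on its baseline score, site and one adherence score. Site is included because Aim 3 allows both adherence and change to differ by site, and such a difference could otherwise appear as an adherence slope.
2. Fix the adherence score before follow-up data are seen. One option is the mean over scheduled sessions of actual/planned duration, capped at 1, with missed sessions as 0. Total minutes is a legitimate alternative. If planned length is used, it should be each participant's own, since section 1.3.7 says "Level of increase will be individually based". Say whether absences exempted for the bonus count as scheduled sessions.
3. Report every adherence slope with a 95% CI and make no significance claims.
4. State that the slope is confounded by self-selection, limited to people with follow-up data, and imprecise.

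**Route B: delete the adherence clause** from the Aim 2 hypothesis in section 1.0.

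**With either route**, reword the Aim 2 statement and the SAP preamble so that the purpose is to estimate pre-post change over 12 weeks. State that, with no control group and a repeated battery, the change cannot be attributed to exercise.

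**Cost.** Route A needs one SAP paragraph and one regression per outcome, about 13, with no new participant measures. The planned-length score also requires planned session length to be stored, because the transferred data listed in section 1.1.12 include actual duration only; total minutes needs nothing extra. Route B costs one deletion. The rewording is two edits and gives a weaker headline claim.
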